### 3.3 Early Withdrawal of Subjects

#### 3.3.1 Criteria for removal from study

Insert subject withdrawal criteria (e.g., safety reasons, failure of subject to adhere to protocol requirements, subject consent withdrawal, disease progression, etc.).

Failure to comply with study procedures.

Participant withdraws consent.

### 3.3.2 Follow-up for withdrawn subjects

Describe when and how to withdraw subjects from the study; the type and timing of the data to be collected for withdrawal of subjects; whether and how subjects are to be replaced; the follow-up for subjects withdrawn from investigational treatment.

No safety concerns; no reason for follow-up. If consent is withdrawn no data from the participant will be used. Otherwise, if consent is not withdrawn, data from individuals who withdraw from the study may be used in an intent-to-treat analysis but another individual will be enrolled to ensure that an adequate sample size (with complete data) is reached.

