## 8.0 Subject Numbers and Statistical Plan

### 8.1 Number of Subjects

Indicate the total number of subjects to be accrued.

If applicable, distinguish between the number of subjects who are expected to be enrolled and screened, and the number of subjects needed to complete the research procedures (i.e., numbers of subjects excluding screen failures.)

Approximately 135 subjects will complete the screening process for this study; of those we anticipate 59 subjects to be eligible A total of 45 participants will complete the study. To achieve this, we will likely need to randomize 59 subjects assuming a 30% drop out rate.

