### 8.2 Sample size determination

If applicable, provide a justification of the sample size outlined in section 8.1 – to include reflections on, or calculations of, the power of the study.

To provide 80% power ( $p<0.05$ ) to detect a minimum 10 mg/dL difference in fasting glucose between the treatments, 45 participants are required (standard deviation of 23.4mg/dL). To account for a 30% drop-out rate, 59 subjects will be randomized. Completion of 45 subjects will also provide 80% power ( $p<0.05$ ) to detect a minimum 11 mg/dL (standard deviation 25.9 mg/dL) difference between the treatment in LDL-cholesterol, and a 4.5 mmHg difference in systolic blood pressure (standard deviation 11 mmHg).

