### 8.3 Statistical methods

Describe the statistical methods (or non-statistical methods of analysis) that will be employed.

The normality of the data will be tested before performing analyses, and transformations will be made if needed. Mixed effect models will be used to determine between-group changes over time and between group differences in mean values following the treatments. Treatment will be included as a fixed effect. Subject will be included as a random effect.

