#### **9.1.4 Transferring Data and/or Specimens**

If the data and/or specimens will be transferred to and/or from outside collaborators, identify the collaborator to whom the data and/or specimens will be transferred and how the data and/or specimens will be transferred. This information should not conflict with information provided in section 9.1.1.1 regarding who has access to identifiable information, if applicable.

After collection, serum and plasma are transferred to ~1 mL aliquots – these vials contain only the participants study ID #, sample type (serum or plasma) and time point. The vials are then boxed and stored in a locked -80 degree freezer until all data collection is complete. Fecal samples will also be stored in a locked -80 degree freezer and the vials will contain no identifying information. Once the study is complete the samples will be sorted and

shipped on dry ice via FedEx or a Quest Courier to the following sites for analysis: (No identifying information is provided with the samples)

Serum/Plasma:

- Quest diagnostics, [name]

Fecal samples:

- Wright Labs LLC, [name]

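### Does leaving the primary analysis set unnamed make the glucose comparison a completer-only one?

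*Combined protocol and SAP*

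**What the plan says.** Section 3.3.1 gives two grounds for removal: withdrawal of consent, and "Failure to comply with study procedures". Section 3.3.2 then treats the two kinds of leaver differently. For the first, "If consent is withdrawn no data from the participant will be used". For the others, "data from individuals who withdraw from the study may be used in an intent-to-treat analysis but another individual will be enrolled", and the stated aim of that replacement is "to ensure that an adequate sample size (with complete data) is reached".

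Section 8.3 plans mixed models for changes over time and for post-treatment means: "Treatment will be included as a fixed effect. Subject will be included as a random effect". It names no analysis population and no missing-data assumption, and no other section does so.

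On numbers, Section 8.1 says "A total of 45 participants will complete the study", and Section 8.2 says "To account for a 30% drop-out rate, 59 subjects will be randomized". Section 9.1.4 adds that blood samples are "stored in a locked -80 degree freezer until all data collection is complete".

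**The concern.** Two analysts could follow this text faithfully and report different primary results, one from completers and one from all available data. Replacement aimed at complete data, and a sample size counted in completers, seem to lean towards the first reading.

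One ground for removal is non-compliance. A completer-only set would therefore be selected after randomisation on behaviour that the assigned snack may influence. Section 11.0 expects some gastrointestinal upset from the test foods and allows for an unrecognised food allergy, so loss that differs by snack is plausible. A completer-only result would describe people who finish both snacks, and it would discard end-of-period-1 glucose values that the model can use. If the set were settled only after the assays came back, the choice could also be influenced by the results.

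**Working it through.** **1. The plan's own figure.** Section 8.2 gives a difference of 10 mg/dL, an SD of 23.4 mg/dL, 80% power and p<0.05 (taken as two-sided). For a paired comparison the normal approximation is n = (23.4 × (1.960 + 0.842) / 10)² = 42.98, so 43. The exact paired t-test needs 45, with power 80.06%. The stated 45 is reproduced if 23.4 is the SD of the within-person difference. The trial is therefore powered on completers, and replacement protects that count whichever set is analysed.

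**2. How many people are involved.**
- As planned: 59 − 45 = 14 leavers (23.7%).
- With a true 30% loss and replacement up to 45 completers: 45 / 0.70 = 64.3, so 65 randomised and 20 leavers.
- Stopping at about 41 completers (59 × 0.70 = 41.3) is not an end state under Section 3.3.2, because replacement continues.

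**3. What the planned model does with a leaver.** A random-effects model does not need both periods. A participant with an end-of-period-1 value contributes through the between-person comparison. Excluding that person takes a deliberate step that the plan nowhere prescribes.

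**4. Information gained by keeping leavers.** The documents give no within-person correlation ρ, so 0.3 to 0.9 is assumed. Let n be the completers, and m the leavers with a period-1 value, balanced by treatment.
- Completers supply information n / [2σ²(1 − ρ)].
- Leavers, using end values only, supply m / (4σ²).
- Ratio of total to completer-only information: 1 + m(1 − ρ) / (2n).

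Sections 7.1 and 7.2.2 also give glucose at the start of each period, and Section 8.3 plans changes over time. With equal correlation across all four occasions, a leaver's end value has residual variance σ²(1 − ρ²) given the start value. Leavers then supply m / [4σ²(1 − ρ²)], and the ratio is 1 + m / [2n(1 + ρ)].

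| ρ | 45+14, end only | 45+20, end only | 45+14, with start | 45+20, with start |
|---|---|---|---|---|
| 0.3 | 1.109 | 1.156 | 1.120 | 1.171 |
| 0.5 | 1.078 | 1.111 | 1.104 | 1.148 |
| 0.7 | 1.047 | 1.067 | 1.092 | 1.131 |
| 0.9 | 1.016 | 1.022 | 1.082 | 1.117 |

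Adding a period term, which Section 8.3 does not list, leaves the balanced end-only ratios unchanged.

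**5. In mg/dL.** The completer-only standard error is 23.4 / √45 = 3.49. The largest gain in the table gives 3.49 / √1.171 = 3.22, and the smallest gives 3.49 / √1.016 = 3.46.

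**6. Why these are ceilings.** They need every leaver to have reached the end of period 1 and nobody to have withdrawn consent. If only 7 of 14 leavers have a usable value, the end-only ratio is 1 + 7(1 − ρ)/90, which is 1.054 at ρ = 0.3 and 1.008 at ρ = 0.9. If all 14 had the same period-1 treatment, generalised least squares with a period term gives 1.083 to 1.012.

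**The case for a change.** The strongest case for a change is that permission is not a commitment. The planned model can use leavers' data, but no sentence requires it, and the intent-to-treat analysis in Section 3.3.2 is not called primary. Freezing the samples hides study glucose results while people are leaving, but it does not stop the set from being picked after the assays. Writing the set down would cost a few lines.

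Much of this stands: the text is silent, and nothing in it fixes the timing of the choice. But that is an argument for fuller documentation. It does not show that a stated rule gives a wrong answer.

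Naming a set would also not remove the selection complained of. A set defined by at least one end-of-period glucose is itself formed after randomisation. It omits everyone who leaves during period 1 and everyone whose data are barred by withdrawal of consent, and Section 3.3.2 plans no follow-up that could recover their outcomes. The only alteration to a stated rule would be to keep data collected before consent was withdrawn. That depends on the consent form and the IRB's position, neither of which is in the reviewed text.

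**Conclusion.** No change follows. This is missing detail that a competent analyst fills sensibly: the model in Section 8.3 takes all available records, and Section 3.3.2 names intent-to-treat for leavers whose consent stands. Replacement adds participants and removes nobody. Completer-only analysis is permitted but not prescribed, and power for 10 mg/dL is met on completers alone.

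In precision, the choice moves the standard error from 3.49 mg/dL to no lower than about 3.22 under the most favourable assumptions examined. This rests on 23.4 mg/dL being the SD of the within-person difference, on assumed correlations of 0.3 to 0.9, on equal correlation across occasions, and on leavers balanced by treatment.

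Two quantities stay unknown: the selection bias in a completer-only estimate, and the dilution from including non-compliant participants. The documents give neither the timing of nor the reasons for drop-out, so neither can be sized. A reader of the eventual report should check which set was analysed and how withdrawals fell by snack and sequence.

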## 4.0 Recruitment Methods

### 4.1 Identification of subjects

Describe the methods that will be used to identify potential subjects or the source of the subjects. If not recruiting subjects directly (e.g., database query for eligible records or samples) state what will be queried, how and by whom.

StudyFinder: If you intend to use StudyFinder (<http://studyfinder.psu.edu>) for recruitment purposes, please indicate this in section 4.1 along with any other methods for identifying subjects. Note that information provided in this protocol should be consistent with information provided on the StudyFinder page in your CATS IRB study.

For Penn State Hershey submissions using Enterprise Information Management (EIM) for recruitment, attach your EIM Design Specification form on the Basic Information page in CATS IRB (<http://irb.psu.edu>). See HRP-103 Investigator Manual, "What is appropriate for study recruitment?" for additional information.

Flyer/posters will be placed in campus buildings and facilities as well as the surrounding area (gyms, churches, supermarkets, coffee shops etc.) to identify potential subjects residing in and around the State College. Ads will also be placed in the local papers, magazines (e.g Centre Daily Times) and coupon mailers (e.g. Valpak), which are distributed to residential homes. In addition, radio ads will be run. Websites (e.g. <http://clinicaltrials.gov/>, Facebook, Craig's List), and PSU listservs will be used to advertise the study. We also will contact individuals who have participated in previous studies and indicated to our research group that they are interested in participating in future studies. A letter to local businesses or organization may be utilized requesting they share study details with their members/employees if permitted.

### 4.2 Recruitment process

Describe how, where and when potential subjects will be recruited (e.g., approaching or providing information to potential subjects for participation in this research study).

Public advertisements (flyers/posters/ newspaper ads/circulars/ websites and social media/ radio) in the local community (State College/ University Park area) will be used to recruit people. These ads will be run periodically depending on recruitment. When an individual responds to an ad, study staff will contact the individual using the contact details provided.

A letter to local businesses or organization may be utilized requesting they share study details with their members/employees if permitted.

All of these methods of recruitment will be used until the target sample size is reached.

#### 4.3 Recruitment materials

List the materials that will be used to recruit subjects. Add recruitment documents to your study in CATS IRB (<http://irb.psu.edu>) on the “Consent Forms and Recruitment Materials” page. For advertisements, upload the final copy of printed advertisements. When advertisements are taped for broadcast, attach the final audio/video tape. You may submit the wording of the advertisement prior to taping to preclude re-taping because of inappropriate wording, provided the IRB reviews the final audio/video tape.

StudyFinder: If you intend to use StudyFinder (<http://studyfinder.psu.edu>) for recruitment purposes, you do not need to upload a separate recruitment document for information placed on the StudyFinder site to your study in CATS IRB. Necessary information will be captured on the StudyFinder page in your CATS IRB study.

Flyer and print ad (used for Newspaper and Magazine advertisement, circular ads, websites)  
PSU Newswire, email, or list-serve advertisement

Letter: a letter to local businesses or organizations may be utilized requesting they share study details with their members/employees.

Radio ad

#### 4.4 Eligibility/screening of subjects

If potential subjects will be asked eligibility questions before obtaining informed consent, describe the process. Add the script documents and a list of the eligibility questions that will be used to your study in CATS IRB (<http://irb.psu.edu>) on the “Consent Forms and Recruitment Materials” page.

StudyFinder: If you intend to use StudyFinder (<http://studyfinder.psu.edu>) for recruitment purposes, any scripts (phone, email, or other) used when contacting StudyFinder participants as well as any eligibility screening questions must be added to your study in CATS IRB (<http://irb.psu.edu>) on the “Consent Forms and Recruitment Materials” page.

Potential subjects who have responded to advertisements will be asked eligibility questions via a telephone screening before informed consent is obtained (refer to telephone screening form for complete list of screening questions). If you do not qualify for the study, the general reason why you did not qualify for the study will be recorded under an assigned screening study ID#.

Documents containing information gathered during the telephone screening will be stored in a locked cabinet in 317 Chandlee lab or in a password protected file on a secure network. If you do qualify for the study, information gathered during the telephone screening such as names, addresses, telephone numbers, email addresses, date of birth, and visit dates will be linked to data via a code break list. Once enrolled in the study, all data collection will be performed under an assigned study ID# that is known only to the principal investigators, study coordinators and CRC staff (for purposes of blood collection and safety). These are the only persons able to connect the participant's identifiable information.

### 5.0 Consent Process and Documentation

Refer to “SOP: Informed Consent Process for Research (HRP-090)”, for information about the process of obtaining informed consent from subjects. HRP-090 can be accessed by clicking the Library link in CATS IRB (<http://irb.psu.edu>).

#### 5.1 Consent Process

## 5.1.1 Obtaining Informed Consent

### 5.1.1.1 Timing and Location of Consent

Describe where and when the consent process will take place.

After a brief telephone conversation explaining the study and answering some preliminary screening questions, a screening appointment will be scheduled at the Clinical Research Center (CRC). At this appointment, before any procedures take place, potential participants will be given the informed consent document. Following standard protocol procedure, a trained staff person will review the information in detail, make sure the individual understands the study and answers any questions they may have. If the participant is still interested in continuing with the screening process, both the participant and the staff member will sign and date the document. A copy of the signed consent document will be provided to the participant.

### 5.1.1.2 Coercion or Undue Influence during Consent

Describe the steps that will be taken to minimize the possibility of coercion or undue influence in the consent process.

Study staff, coordinators, and investigators who are fully trained in the recruiting process will respond to potential participants during recruitment so as to avoid any coercion or undue influence.

## 5.1.2 Waiver or alteration of the informed consent requirement

If you are requesting a waiver or alteration of consent (consent will not be obtained, required information will not be disclosed, or the research involves deception), describe the rationale for the request in this section. If the alteration is because of deception or incomplete disclosure, explain whether and how subjects will be debriefed. Add any debriefing materials or document(s) to your study in CATS IRB (<http://irb.psu.edu>) on the "Supporting Documents" page. NOTE: Review the "CHECKLIST: Waiver or Alteration of Consent Process (HRP-410)" to ensure you have provided sufficient information for the IRB to make these determinations. HRP-410 can be accessed by clicking the Library link in CATS IRB (<http://irb.psu.edu>).

Not applicable

## 5.2 Consent Documentation

### 5.2.1 Written Documentation of Consent

Refer to "SOP: Written Documentation of Consent (HRP-091)" for information about the process to document the informed consent process in writing. HRP-091 can be accessed by clicking the Library link in CATS IRB (<http://irb.psu.edu>).

If you will document consent in writing, describe how consent of the subject will be documented in writing. Add the consent document(s) to your study in CATS IRB (<http://irb.psu.edu>) on the "Consent Forms and Recruitment Materials" page. Links to Penn State's consent templates are available in the same location where they are uploaded and their use is required.

At their scheduled screening clinic appointment, before any procedures take place, potential participants will be given the informed consent document. Trained research personnel will make sure the individual understands the study expectations and will answer any questions they

may have. If the participant still is interested in continuing with the screening process, both the participant and the staff member will sign and date the document. A copy of the consent document will be provided to the participant. Signed original copies will be kept on file by the PI.

### **5.2.2 Waiver of Documentation of Consent (Implied consent, Verbal consent, etc.)**

If you will obtain consent (verbal or implied), but not document consent in writing, describe how consent will be obtained. Add the consent script(s) and/or information sheet(s) to your study in CATS IRB (<http://irb.psu.edu>) on the “Consent Forms and Recruitment Materials” page. Links to Penn State’s consent templates are available in the same location where they are uploaded and their use is required. Review “CHECKLIST: Waiver of Written Documentation of Consent (HRP-411)” to ensure that you have provided sufficient information. HRP-411 can be accessed by clicking the Library link in CATS IRB (<http://irb.psu.edu>).

If your research presents no more than minimal risk of harm to subjects and involves no procedures for which written documentation of consent is normally required outside of the research context, the IRB will generally waive the requirement to obtain written documentation of consent.

Verbal consent to participant in the telephone screening will be obtained. The telephone screening involves minimal risk and involves no procedures for which written documentation of consent is normally required outside of the research context. The questions asked are only those needed to ascertain whether a person may be eligible for the study and include contact details, and yes or no responses to a number of questions about dietary habits, food allergies, medical history and lifestyle. Thus, the only risk is that of minor discomfort when being asked questions related to lifestyle and personal medical history.

## **5.3 Consent – Other Considerations**

### **5.3.1 Non-English Speaking Subjects**

Indicate what language(s) other than English are understood by prospective subjects or representatives.

If subjects who do not speak English will be enrolled, describe the process to ensure that the oral and written information provided to those subjects will be in that language. Indicate the language that will be used by those obtaining consent.

Indicate whether the consent process will be documented in writing with the long form of the consent documentation or with the short form of the consent documentation. Review the “SOP: Written Documentation of Consent (HRP-091)” and the “Investigator Manual (HRP-103)” to ensure that you have provided sufficient information. HRP-091 and HRP-103 can be accessed by clicking the Library link in CATS IRB (<http://irb.psu.edu>).

Not applicable

### **5.3.2 Cognitively Impaired Adults**

Refer to “CHECKLIST: Cognitively Impaired Adults (HRP-417)” for information about research involving cognitively impaired adults as subjects. HRP-417 can be accessed by clicking the Library link in CATS IRB (<http://irb.psu.edu>).

#### **5.3.2.1 Capability of Providing Consent**

Describe the process to determine whether an individual is capable of consent.

Not applicable.

#### **5.3.2.2 Adults Unable To Consent**

Describe whether and how informed consent will be obtained from the legally authorized representative. Describe who will be allowed to provide informed consent. Describe the process used to determine these individual's authority to consent to research.

For research conducted in the state, review "SOP: Legally Authorized Representatives, Children and Guardians (HRP-013)" to be aware of which individuals in the state meet the definition of "legally authorized representative". HRP-013 can be accessed by clicking the Library link in CATS IRB (<http://irb.psu.edu>).

For research conducted outside of the state, provide information that describes which individuals are authorized under applicable law to consent on behalf of a prospective subject to their participation in the procedure(s) involved in this research. One method of obtaining this information is to have a legal counsel or authority review your protocol along with the definition of "children" in "SOP: Legally Authorized Representatives, Children, and Guardians (HRP-013)." HRP-013 can be accessed by clicking the Library link in CATS IRB (<http://irb.psu.edu>).

Not applicable.

